# TRIAL FLOW CHART – ( Mental Health Cluster) ANTENATAL MOTHERS

At antenatal period (after 12 weeks pregnancy during first booking visit), a batch of 100 mothers who happen to have the booking appointment at the time of distribution of the screening sheets are asked to complete the Phase I assessment including brief Demographic Data, Whooley Questions & Relationship Questions. Screening sheets sent by post prior to first booking appointment.

Mothers with no Mental Health Difficulties receive treatment as usual from Gynae and Obs. Mothers with Mental Health Difficulties are asked by the recruiter, normally a midwife to complete Phase II assessment (including EPDS, GAD7, R-DAS, ANRQ). Those scoring for anxiety and/or depression are assessed through the MINI for a diagnosis by psychiatrist/clinical psychologist making use of the MINI

Antenatal mothers who are diagnosed with anxiety or depression and are willing to participate in the RCT, will form part of the Mental Health Cluster of this study. 60 mothers will be randomised:

- a. 30 in intervention group
- b. 30 in control group

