## **Intervention Group Mothers are offered:**

- a. Assessment by Psychiatrist and medication (if indicated) and follow-up
- b. 12 Psychotherapy sessions online (5 weekly/7 bi-weekly)
- c. A Monthly phone call by midwife over the 5 month period.

Post-intervention period (19 weeks), Control and Intervention Group mothers given EPDS, GAD7, DAS-R, once again. Mothers requiring psychiatric attention continue to be followed by psychiatrist and midwife throughout the 8-week period and beond as necessary.

As per **TIDier checklist** the intervention for first cluster on Mental Health Difficulties will be as follows:

- 1. Name of intervention: 12 psychotherapy sessions over 19 weeks (the first five sessions on a weekly basis in the first five weeks, and the remaining seven sessions taking place fortnightly. In addition to assessment of a psychiatrist and medication if indicated plus 5 monthly phone calls by midwife.
- 2. Why this intervention: The reason for choosing the psychotherapeutic sessions is based on literature that suggests that psychotherapy whether it is interpersonal, cognitive behavioural or non directive is helpful. Pearson (2008) reports that psychotherapy especially interpersonal therapy has been found to be effective in the case of antenatal depression for mothers., whereas Misri et al (2015) also recommend psychotherapy and mindfulness for those mothers suffering from anxiety. Considering the current training of family therapists in Malta and their subsequent employment within the health service, we also wanted to find out whether family therapists trained in systemic psychotherapy would be able to support antenatal mothers effectively in the case of antenatal depression or anxiety.
- 3. What does intervention consist of: a total of 12 sessions of psychotherapy lasting a maximum of one hour each will be given to those parents indicated as showing mental health difficulties.
- 4. The psychotherapy may take different formats such as individual sessions for those presenting with depression and/or anxiety, couple therapy for those with anxiety and or depression and a strained couple relationship.
- 5. Procedure used in intervention: Participants who have been randomised into the intervention group will be offered a set of 12 appointments for sessions which would need to take place over a period of 19 weeks with their designated therapist.

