- 3. Analysis of covariance (ANCOVA) of post-intervention scores with baseline score as the covariate. This approach differs subtly from the two mentioned above. Analysis of covariance treats the pre-test value as a covariate that can be a source of variation that may influence post-test scores, and accordingly the post-test score is regressed on both the pre-test score and the grouping variable. ANCOVA adjusts the pre-test scores, increasing the power to determine whether or not there has been a treatment effect. This approach tests the null hypothesis of no difference between the control and treatment post.

Should the results indicate that there has been significant improvement at post-testing, one should also evaluate for any differences in the change of scores between the two groups through stepwise linear regression using a bootstrapping procedure with 5000 replications recommended for analyses with smaller sample sizes (Preacher and Hayes, 2008). Groups alone will be included in Model 1, and any confounds that differed across the two groups at baseline will be included in Model 2, allowing for the comparison of the effect size as a function of study condition in unadjusted and adjusted models. Results will be determined to be statistically significant if p values were <0.05.

Furthermore, it would be of interest to see whether there is an association between a high score in ANRQ and the incidence of depression and anxiety. Thus, the idea is to check for any possible correlation between ANRQ and EPDS and ANRQ and GAD-7 for both pre- and post-testing, through the Pearson correlation or alternatively the Spearman correlation, if the assumption of normality is not satisfied.

The assumption of normality to perform all the above tests will be evaluated by the Shapiro-Francia test. If the assumption of normality has been violated, the p-value will be less than 0.05. If the assumption of normality has not been violated, the p-value will be greater than 0.05. This is because the Shapiro-Wilk test is evaluating the null hypothesis that the distribution of the data is equal to a normal distribution. Rejecting the null hypothesis means that the distribution of the data is not equal to a normal distribution.

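### The exploratory post-test ANRQ correlations should control for randomised arm; if the arms are pooled, a therapy effect modestly dilutes them

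*Protocol*

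**What the plan says.** The last analysis described under Analytic Methods in the protocol concerns the Antenatal Risk Questionnaire (ANRQ). It is introduced as exploratory: "it would be of interest to see whether there is an association between a high score in ANRQ and the incidence of depression and anxiety". The method is to "check for any possible correlation between ANRQ and EPDS and ANRQ and GAD-7 for both pre- and post-testing". The coefficients are to be obtained "through the Pearson correlation or alternatively the Spearman correlation, if the assumption of normality is not satisfied". Both are two-variable coefficients. The text mentions no adjustment for arm, no partial correlation and no split by arm.

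The ANRQ is collected before randomisation. The trial flow chart has mothers with difficulties "complete Phase II assessment (including EPDS, GAD7, R-DAS, ANRQ"), and the Measures section places all pre-measures ahead of allocation. At 19 weeks the protocol has "Control and Intervention Group mothers given EPDS, GAD7, DAS-R, once again"; the ANRQ is not in that list. The post-test correlations therefore relate baseline ANRQ to scores taken after one arm has been offered 12 therapy sessions and the other has not.

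Trial Design states the hypothesis that intervention mothers will score lower than controls on EPDS and GAD-7.

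**The concern.** One method is applied at two time points where the data differ in structure. Before randomisation, the mothers form one group with respect to treatment. At 19 weeks they are two groups that the trial expects to have different mean scores.

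If the 60 mothers are pooled at that point, the gap between the arm means becomes part of the outcome variance. Randomisation makes ANRQ independent of arm in expectation, so this extra variance has nothing to do with ANRQ and pulls the coefficient towards zero. The larger a uniform therapy effect, the stronger the pull. At stake is some sensitivity in a secondary question about the ANRQ, not the evidence on therapy.

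**Working it through.** The protocol gives no target correlation, effect size or power for this analysis, so there is no figure of its own to reproduce.

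**Inputs from the protocol**
- Sample: "60 mothers will be randomised", with "30 in intervention group" and 30 in control (trial flow chart).
- Significance: "Results will be determined to be statistically significant if p values were <0.05" (Analytic Methods), taken here as two-sided.
- ANRQ measured before randomisation, so independent of arm in expectation.

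**Assumed inputs**
- Therapy effect d, in within-arm standard deviations: 0.3 to 1.5.
- Within-arm correlation rho: 0.3 for the main illustration, the same in both arms.
- All 60 mothers have post-test scores.

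**Step 1: dilution.** With equal arms and within-arm variance 1, the pooled outcome variance is 1 + d²/4. The covariance with ANRQ is unchanged in expectation. Hence pooled r = rho / sqrt(1 + d²/4). For d = 0.8 this is 0.3 / sqrt(1.16) = 0.279. The formula is for the Pearson coefficient.

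**Step 2: power, by Fisher's z.**
- Pooled: Φ(atanh(pooled r) × sqrt(57) − 1.96).
- Arm-adjusted: Φ(atanh(rho) × sqrt(56) − 1.96) = Φ(0.3095 × 7.483 − 1.96) = 0.639, whatever d is.

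| d (assumed) | Factor | Pooled r (rho = 0.3) | Power, pooled | Power, arm-adjusted |
|---|---|---|---|---|
| 0.3 | 0.989 | 0.297 | 0.637 | 0.639 |
| 0.5 | 0.970 | 0.291 | 0.619 | 0.639 |
| 0.8 | 0.928 | 0.279 | 0.579 | 0.639 |
| 1.0 | 0.894 | 0.268 | 0.546 | 0.639 |
| 1.5 | 0.800 | 0.240 | 0.455 | 0.639 |

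**Step 3: simulation.** With rho = 0.3 and 20,000 trials of 30 + 30, the mean pooled r was 0.290, 0.276 and 0.266 at d = 0.5, 0.8 and 1.0, against 0.298 with arm removed. A separate simulation with rho = 0.35 and 8,000 runs gave power of 0.769, 0.731 and 0.695 pooled, against 0.788, 0.791 and 0.787 adjusted. With no true correlation, both methods rejected in about 5% of runs.

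**Step 4: scale.** The sampling standard deviation of r in the simulation was about 0.12, and the 95% interval around r = 0.3 with 60 mothers is 0.05 to 0.515. The loss up to d = 1.0 is about 0.03 (0.300 − 0.268 = 0.032), roughly a quarter of that standard deviation.

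**Step 5: if the link itself differs by arm.** Suppose the correlation is 0.5 in controls and 0.1 in treated mothers, with d = 0.8. The pooled value is about (0.5 + 0.1)/2 × 0.928 = 0.28, which matches neither arm. These values are purely illustrative.

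**The case against.** **Pooling is inferred, not stated.** The ANRQ sentence does not say that the arms are combined. Correlations by arm would fit the wording, and the descriptive statistics in the same section are given by group. This stands as a limit on the claim. Against it, the treatment-effect analyses in that section name group explicitly, and the ANRQ sentence does not.

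**Detail of this kind may be left to a statistical analysis plan.** This has some force for an exploratory analysis. But the protocol does name a method, and a better one is available at almost no cost, so the point is an improvement rather than a complaint about missing detail.

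**The effect is small.** This stands. Arm does not confound the correlation in expectation, type I error is unchanged, and the dilution is well within sampling error. Every d and rho is assumed.

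Two stronger readings are tempting and are not supported:
- A reader might infer that the pooled coefficient describes neither treated nor untreated mothers. With a common within-arm correlation it is only a slightly diluted version of that correlation. It would misdescribe both arms only if therapy changed the ANRQ-symptom link, which the protocol neither says nor excludes.
- A reader might infer that a fall in correlation from pre-test to post-test will be mistaken for the ANRQ losing predictive value. The protocol plans no such comparison. Nor is a fall assured: mothers are selected on high EPDS or GAD-7 scores, which can itself depress the pre-test correlation, and therapy that helped low-risk mothers more could strengthen the pooled one.

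**Conclusion.** The point holds as a minor improvement. As most naturally read, the post-test ANRQ correlations leave between-arm variance in the outcome. The cost is 3% to 11% of the coefficient for d from 0.5 to 1.0, and about 2 to 9 percentage points of power when the within-arm correlation is 0.3. This rests on assumed values of d and rho, equal arms, a common within-arm correlation, complete post-test data and the inference that the arms are pooled. No treatment-effect estimate or test is affected, because the planned between-group analyses of EPDS, GAD-7 and R-DAS already include group. The pre-test correlations are not affected either.

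**What to change.** State under Analytic Methods that the association of ANRQ with post-test EPDS and GAD-7 will be estimated by a partial correlation (Pearson or Spearman) controlling for randomised arm. A regression of the post-test score on ANRQ and arm serves the same purpose. Keep the pre-test correlations as planned.

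If coefficients are also shown by arm, label them descriptive. There would be four of them (two scales in two arms), each on 30 mothers, with power of only about 0.36 at a correlation of 0.3. Differences between arms would be mostly noise.

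The cost is one sentence and one degree of freedom, with no new data. On Fisher's z scale the standard error rises by a factor of sqrt(57/56) = 1.009, so little is lost even if therapy has no effect.
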